### 14.1.1.2. Change from baseline to week 24 in the Malmö POTS Symptom Score (MaPS)

The MaPS score consists of 12 questions that will assess symptom burden related (tachycardia, palpitations, dizziness, presyncope) and unrelated to orthostatic intolerance (GI symptoms, insomnia, concentration difficulties). Participants will grade their symptoms for the past 7 days using a 11-point scale ranging from 0 (no symptoms) to 10 (worst possible). The items will be summed to yield a total score with a maximum value of 120 points, with higher scores indicating more severe symptoms. This total score will be derived programmatically.

For change from baseline to week 24 in MaPS score, analysis will be presented similar to analysis proposed for COMPASS 31. Summary statistics will be provided in terms of absolute value and changes from baseline for each visit using FAS for IAWK12 and IAWK24. All data will be included for subject in the IA even if it is for visits after week 12.

For change from baseline to week 24 in MaPS, between treatment group difference will be analyzed using ANCOVA as presented in section 14.1.1.1, except with change from baseline in MaPS as the dependent variable and baseline value of MaPS as covariate.

### 14.1.1.3. Supplementary Analysis of Primary Efficacy Variables

COMPASS 31 questionnaire is to evaluate the severity and distribution of autonomic symptoms in various autonomic nerve disorders. The 31-item questionnaire addresses 6 domains: orthostatic intolerance, vasomotor, secretomotor, bladder, pupillomotor, and gastrointestinal-mixed upper and diarrhea. The original version of COMPASS 31 (longer recall) will be administered at screening and the modified version (2-week recall) will be administered at baseline and all other time points. The modified COMPASS 31 version used in the ARGX-113-2104 study modified the recall period to 2 weeks in contrast with the original COMPASS 31.

Document: BIOSdata\argenx\Efgartigimod\HAB40220\Biostatistics\Documentation\SAP

Author: Version Number: 3.0

Version Date: 02 May 2024

Template No.: CS\_TP\_BS016 Revision 7 Reference: CS\_WI\_BS005

Effective Date: 01Nov2021

argenx Confidential 36

Page 36 of 64

Participants are asked to respond to each of the item question using different, response options depending on each item, based on their perceived symptoms experience over the last 2 weeks. The response options are different depending on item content and vary from dichotomous to 7-point scale options. The modified COMPASS 31 has 6 domains that sum up to a total score of 0 to 100. Higher scores indicate a more severe degree of autonomic symptoms.

The modified COMPASS 31, scoring algorithm for each domain and total scores will be provided by external vendor. This total score will be considered for change from baseline analysis.

The supplementary primary efficacy analysis will be performed for the FAS for IAWK12 and IAWK24. Summary statistics will also be provided in terms of absolute value and changes from baseline for each visit where no imputation performed on missing data.

The estimand uses the composite approach, and is the difference between treatment arms in change from baseline to week 24 in COMPASS-31 and MaPS with outcomes after stopping IMP and /or using prohibited medication imputed as gaining no further benefit over and above that of the control arm.

Treatment Condition: Efgartigimod or placebo assuming less efficacious outcome post ICE Population: Randomized participants with post—COVID-19 postural orthostatic tachycardia syndrome as defined in FAS.

Variable/Endpoint(s): Change from baseline to week 24 in the Composite Autonomic Symptom Score 31/change from baseline to week 24 in the Malmö POTS Symptom Score (MaPS)

Intercurrent Events (ICE): Composite Approach, with Imputation using MNAR model delta adjustment imputation.

Delta adjustment will be applied to only treatment arm and ICE occurred; no delta adjustment will be performed for placebo arm. Any missing data other than ICE in treatment arm will be imputed using MAR assumption. Missing data under placebo arm will be imputed assuming MAR, irrespective of ICEs. The result will be created assuming delta=3, 4, 5. Further sensitivity analysis can be performed with different deltas.

- a. Early discontinuation of study treatment
- b. Use of any prohibited medications

Population-level summary: Change from baseline mean difference between placebo and efgartigimed in COMPASS-31 and MaPS presenting Difference in LS means, corresponding 95% CI and p-value using the FAS.

Document: BIOSdata\argenx\Efgartigimod\HAB40220\Biostatistics\Documentation\SAP

Author: Version Number: 3.0

Version Date: 02 May 2024

Template No.: CS\_TP\_BS016 Revision 7 Reference: CS\_WI\_BS005

Effective Date: 01Nov2021

Page 37 of 64

ICE	Approach for dealing with the ICE
Discontinuation of study treatment	Composite approach: scores after treatment discontinuation in participants who discontinue treatment and refused to stay in the study will in the case of both the experimental arm and the control arm be imputed being modelled as gaining no further benefit over and above that of the control arm.
Use of any prohibited medication	Composite approach: assessments after visit x, if the ICE has taken place at visit x will in the case of both the experimental arm and the control arm be imputed being modelled as gaining no further benefit over and above that of the control arm.

Explicit details regarding the imputation of missing values are provided via sample SAS code that is intended to demonstrate the application of these strategies. Minor alterations to SAP code may be performed. Example code for generating the missing imputed data is as follows:

Identify ICE 1 and ICE 2,

Seperate patient and ICE, this data will be mergred before applying MNAR

perform MI using MCMC, to impute only the non-monotone missing values (IMPUTE=MONOTONE)

PROC MI DATA=DIA NIMPUTE=500 SEED=9453 OUT=DIA mono;

VAR trt BASVAL change\_1-change\_4;

MCMC CHAIN=SINGLE NBITER=200 NITER=100 IMPUTE=MONOTONE;

RUN;

Merge ICEs patient wise

Apply MAR for Placebo treated patient with or without ICE it will be

PROC MI DATA=DIA\_mono\_(where=(trt=0)) NIMPUTE=1 SEED=4648 OUT=DIA\_imputed\_MAR;

by \_imputation\_;

VAR trt BASVAL change 1-change 4;

CLASS trt;

MONOTONE REGRESSION;

RUN;

Document: BIOSdata\argenx\Efgartigimod\HAB40220\Biostatistics\Documentation\SAP

Author: Version Number: 3.0

Version Date: 02 May 2024

Template No.: CS\_TP\_BS016 Revision 7 Reference: CS\_WI\_BS005

Page 38 of 64

Apply MNAR only for those ICE under treatment arm who have intercurrent event other than 'study treatment discontinuation'.

If the above methodology is unable to be undertaken due to the small sample sizes expected at week 12 analysis or subsequently at week 24, the ANCOVA analysis will be undertaken on observed data only, For the change from baseline to 24 weeks for both the COMPASS 31 analysis an ANCOVA will also be calculated using the FAS by the Proc Mixed procedure, example code is:

```
Ods output estimates =est;
proc mixed data=COMPASS31 method=REML;
class BCOMPASS31 ARMCD;
model change = BCOMPASS31 ARMCD /solution;
LSMEANS trt / diff=control('0') cl;
ODS OUTPUT Diffs=lsdiffs LSMeans=lsm solutionF=Parms;
BY visit _imputation_;
run;
(i.e using week 24 data only.)
```

Combine the imputations using proc MIanalysis

```
proc\ mianalyze\ parms (class var=full) = lsdiffs;
```

BY visit;

class trt;

modeleffects trt;

ods output ParameterEstimates=MIAN lsdiffs;

run;

Document: BIOSdata\argenx\Efgartigimod\HAB40220\Biostatistics\Documentation\SAP

Author: Version Number: 3.0

Version Date: 02 May 2024

Template No.: CS\_TP\_BS016 Revision 7 Reference: CS\_WI\_BS005

Effective Date: 01Nov2021

Copyright © 2009, 2010, 2012, 2016, 2018, 2019, 2021 IQVIA. All rights reserved. The contents of this document are confidential and proprietary to IQVSystatingselrsicand ItsOsluStataries Alphanthocided Visas IdisObDureVoVraQiodIDEureVoVraQiodIDEureVoVraQiodIDEureVoVraQiodIDEureVoVraQiodIDEureVoVraQiodIDEureVoVraQiodIDEureVoVraQiodIDEureVoVraQiodIDEureVoVraQiodIDEureVoVraQiodIDEureVoVraQiodIDEureVoVraQiodIDEureVoVraQiodIDEureVoVraQiodIDEureVoVvraQiodIDEureVoVraQiodIDEureVoVraQiodIDEureVoVraQiodIDEureVoVraQiodIDEureVoVraQiodIDEureVoVraQiodIDEureVoVraQiodIDEureVoVraQiodIDEureVoVraQiodIDEureVoVraQiodIDEureVoVraQiodIDEureVoVraQiodIDEureVoVraQiodIDEureVoVraQiodIDEureVoVraQiodIDEureVoVraQiodIDEureVoVVraQiodIDEureVoVraQiodIDEureVoVraQiodIDEUreVoVraQiodIDEUreVoVraQiodIDEUreVoVraQiodIDEUreVoVVVraQiodIDEUreVoVVVV

Page 39 of 64

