### For the Main estimand:

The available data occurring on or after ICEs will be analyzed as observed (Treatment policy). The reasoning of treatment policy is to estimate the COMPASS-31 and MaPS response based on the available data and data will be analyzed as it is (regardless of the intercurrent event occurring).

For Supportive analysis of estimands

Document: BIOSdata\argenx\Efgartigimod\HAB40220\Biostatistics\Documentation\SAP

Author: Version Number: 3.0

Version Date: 02 May 2024

Template No.: CS\_TP\_BS016 Revision 7 Reference: CS\_WI\_BS005

Page 15 of 64

Composite Variable strategy: Assessment on or after ICEs will be treated missing and imputed assuming MNAR delta adjustment imputation. The rationale behind composite strategy is, discontinue of study treatment or use of prohibited medications will affect the COMPASS-31 and MaPS response.

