### 3.4. Changes to Analysis from Protocol

The protocol mentions mixed model repeated measures as the method of analyzing the Primary endpoints, however the protocol does not mention estimands or Intercurrent events. The SAP considers estimands and intercurrent events. As a result, the main analysis method will be using the mixed model repeated measures and ANCOVA after applying MNAR to missing data from the intercurrent events will be used as supplementary analysis.

The baseline for Questionnaire responses will be the final assessment before the initial administration of IMP up until 3 days post IMP, recorded under baseline visit. The information obtained through this method will be used to inform the development of Phase 3 trials.

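### SAP 14.1.1.3 gives three incompatible rules on which efgartigimod participants with an intercurrent event receive the delta penalty in the supplementary analysis

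*SAP*

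**What the plan says.** SAP 14.1.1 and Table B define two intercurrent events (ICEs): early discontinuation of study treatment and use of any prohibited medication. The supplementary analysis treats them as follows.

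- **SAP Section 2, supportive analysis after Table B:** "Assessment on or after ICEs will be treated missing and imputed assuming MNAR delta adjustment imputation". The rationale given there names both events. No arm is specified.
- **SAP 3.4:** "ANCOVA after applying MNAR to missing data from the intercurrent events will be used as supplementary analysis". Neither event is excluded.
- **SAP 14.1.1.3, estimand statement:** outcomes after either event are "imputed as gaining no further benefit over and above that of the control arm". The treatment condition is worded differently: "Efgartigimod or placebo assuming less efficacious outcome post ICE". Neither phrase mentions a delta.
- **SAP 14.1.1.3, text on ICEs:** "Delta adjustment will be applied to only treatment arm and ICE occurred; no delta adjustment will be performed for placebo arm". Treatment discontinuation is the first of the two events listed beneath it. In the efgartigimod arm, missing at random (MAR) imputation is reserved for data missing for reasons other than an ICE. Then: "The result will be created assuming delta=3, 4, 5" and "Further sensitivity analysis can be performed with different deltas".
- **SAP 14.1.1.3, ICE table:** the discontinuation row covers only those who stop treatment and also decline to remain in the study.
- **SAP 14.1.1.3, programming steps:** "Apply MNAR only for those ICE under treatment arm who have intercurrent event other than 'study treatment discontinuation".

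Protocol 7.1.1 encourages participants who stop treatment to stay in the study. It also lists receipt of a prohibited medication as a circumstance leading to permanent discontinuation of treatment.

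**The concern.** A programmer following the text, the table or the programming steps would penalise three different groups and could report three different estimates from the same data. The programming steps remove the first-listed ICE from the penalty, although the estimand covers it and no reason is given.

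This analysis is the SAP's alternative to the treatment-policy estimand for the primary endpoints, and it is to be reported with a confidence interval and p-value. If discontinuers are exempt, it says little about what happens when stopping treatment is assumed to cost benefit, which is its stated purpose.

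**Working it through.** **Step 1. The three rules side by side (efgartigimod arm).**

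| ICE pattern | Text | Table | Programming step |
|---|---|---|---|
| Stops treatment, leaves study | delta | covered | no delta |
| Stops treatment, stays in study | delta | not addressed | no delta |
| Prohibited medication only | delta | covered | delta |
| Both events | delta | covered by the medication row | unclear |

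The last row matters because of Protocol 7.1.1: someone who receives a prohibited medication is to stop treatment and so would normally have both events. If the programming step excludes anyone who discontinued, almost nobody receives delta, and the results for delta 3, 4 and 5 would hardly differ from MAR. If it excludes only those whose sole event is discontinuation, a few are adjusted. The SAP does not say which.

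**Step 2. What the code settles.** The sample code shows an MCMC step to reach a monotone pattern and a MAR regression step restricted to placebo. There is no code for the delta step and none for MAR imputation in the efgartigimod arm. The steps therefore do not say how the remaining missing values of efgartigimod discontinuers are filled. Nor do they say whether delta is added at week 24 only or at every missing visit.

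**Step 3. Which scores are set to missing.** SAP Section 2 removes assessments at the time of the event and later. The table's prohibited-medication row removes only assessments after the visit of the event. Its discontinuation row is silent on observed scores of those who stay.

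**Step 4. Size per participant.** Inputs: about 42 randomised at 2:1, so 28 and 14 (Protocol 1.1 and 6.3); delta 3, 4, 5 (SAP 14.1.1.3). Higher scores are worse on both instruments, so adding delta reduces apparent benefit. With delta added once at week 24 and covariate adjustment ignored, the shift from k reclassified participants is k × delta / 28. The documents give no ICE counts, so k is assumed.

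| k (assumed) | delta 3 | delta 4 | delta 5 |
|---|---|---|---|
| 1 | 0.11 | 0.14 | 0.18 |
| 3 | 0.32 | 0.43 | 0.54 |
| 6 | 0.64 | 0.86 | 1.07 |
| 8 | 0.86 | 1.14 | 1.43 |

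For discontinuers who stay, this is only the delta part. Replacing an observed score with an imputed one adds a further difference that cannot be sized in advance.

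**Step 5. Yardstick.** The plan's own half-width is blacked out and cannot be reproduced. From Protocol 9.5, SD 15 and correlation 0.8:

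- SD of change = 15 × √(2 × (1 − 0.8)) = 9.49
- SE = 9.49 × √(1/28 + 1/14) = 3.11
- Half-width = 1.96 × SE ≈ 6.09 points (unadjusted, complete data)

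One participant is therefore 0.107/6.09 = 1.8% to 0.179/6.09 = 2.9% of the half-width. Adjusting for baseline, the SD is 15 × √(1 − 0.64) = 9.0 and the half-width about 5.8, which changes little. No SD is given for MaPS, so these percentages apply to COMPASS 31 only.

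**Step 6. Target against method.** If MAR imputation carries over an average benefit B, adding delta d leaves the adjusted participants with a modelled benefit of B − d. That equals the control level only when B = d. A fixed delta therefore matches the wording "Efgartigimod or placebo assuming less efficacious outcome post ICE" in direction, but does not in general deliver the control-level target.

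**The case against.** The strongest reply is that this is one stray sentence and one narrow table row. SAP Section 2, Section 3.4, the estimand statement and the text of 14.1.1.3 all point to both ICEs. The code is labelled as sample code, and minor alterations are allowed. The analysis is supplementary, the shifts are small against the half-width, and the SAP permits an ANCOVA on observed data if samples are too small, so the imputation may never be run. All of that stands and limits the impact. It does not resolve the conflict: the sentence is an explicit restriction, and it is the only one of the programming steps that says who receives the MNAR adjustment.

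A reader might also infer several stronger points that the documents do not support.

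- **The table contradicts the text on placebo.** It does not. The table names both arms but not delta, and MAR imputation of placebo data is compatible with control-level outcomes.
- **The table requires observed scores of discontinuers who stay to be kept.** It is silent on them; SAP Section 2 sets them to missing.
- **Every other section prescribes delta for efgartigimod after either event.** Only the text of 14.1.1.3 says that. Section 2 names no arm, and the estimand statement names no delta.
- **Using the same deltas on a 0–100 and a 0–120 scale is an error.** It is a choice, and the SAP allows further values.

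**Conclusion.** The point holds as an inconsistency within SAP 14.1.1.3. Following the programming step gives zero delta penalty to participants whose only ICE is treatment discontinuation, which is not the stated supplementary estimand. It should be fixed before the analysis is programmed.

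The numerical effect is modest: 0.11 to 0.18 points per reclassified participant, and up to 1.43 points (about 23% of the 6.09 half-width) if eight were reclassified at delta 5. These figures assume 28 efgartigimod participants, delta added at week 24 only, and assumed ICE counts.

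A reader might infer that the trial's main efficacy result is at risk. It is not. The primary mixed model in SAP 14.1.1.1 analyses post-ICE data as observed, and Protocol 9.1 states that no formal hypothesis is tested. The damage is confined to the supplementary analysis.

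**What to change.** 1. In the programming steps, delete the exclusion of treatment discontinuation, so that delta applies to efgartigimod participants with either ICE or both.
2. In the ICE table, remove the condition that discontinuers must also have left the study. The placebo wording can stay.
3. State one rule for which post-ICE scores are set to missing, settling whether the assessment at the visit of the event is included, and use it in Section 2 and in the table.
4. Add code for the efgartigimod delta and MAR steps, and say whether delta is added at week 24 only or at each missing visit.
5. Describe the result as a delta-adjusted analysis assuming a less efficacious outcome after an ICE, and drop the claim of no benefit beyond control. Reference-based imputation or instrument-specific deltas are optional additions.

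The cost is SAP wording and a few lines of imputation code, with no new data or visits. The supplementary estimate may become less favourable. If the Section 2 rule is kept, observed scores of discontinuers who stay are set aside in this analysis only; the primary model still uses them.

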To estimate the difference between the efgartigimod and placebo in mean change from baseline to Week 24, a treatment-by-visit interaction contrast will be constructed (i.e., the treatment group contrast at Week 24). On the basis of this analysis, LS means, SE with 95% CI for placebo and efgartigimod will be reported, along with difference in LS means of efgartigimod vs placebo (with SE), 95% 2-sided CI. 2-sided p-value for testing differences between treatment groups will also be presented. Inference will be based on the precision of the estimation rather than hypothesis testing.

Sample SAS code to be considered as below (SAS code is regarded as "draft" until fully validated at the analysis stage):

```
proc mixed data=COMPASS31 method=REML;
    class BCOMPASS31 ARMCD VISIT USUBJID;
    model change = BCOMPASS31 ARMCD VISIT BCOMPASS* VISIT
    ARMCD*VISIT/ddfm=kenwardroger;
    repeated VISIT / type=un subject = USUBJID;
    lsmeans ARMCD*VISIT / pdiff cl;
    ods output lsmeans = lsm; * contains the adjusted means;
    ods output diffs = dif; * contains treatment differences;
```

Document: BIOSdata\argenx\Efgartigimod\HAB40220\Biostatistics\Documentation\SAP

Author: Version Number: 3.0

Version Date: 02 May 2024

Template No.: CS\_TP\_BS016 Revision 7 Reference: CS\_WI\_BS005

Page 35 of 64

run;

For change from baseline to week 24 in MaPS, between treatment group difference will be analyzed using MMRM, except with change from baseline in MaPS as the dependent variable and baseline value of MaPS as covariate.

The visits included in the model will be weeks 2, 4, 8, 12, 18 and 24.

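### If imputation is judged infeasible, by no stated criterion, the supplementary analysis falls back to an observed-only week 24 ANCOVA that cannot estimate its composite estimand

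*SAP*

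**What the plan says.** The supplementary estimand in SAP 14.1.1.3 follows a composite strategy, with "outcomes after stopping IMP and /or using prohibited medication imputed as gaining no further benefit over and above that of the control arm". Its population is "Randomized participants with post—COVID-19 postural orthostatic tachycardia syndrome as defined in FAS". SAP Section 2, in the text after Table B, gives the handling rule for the supportive analysis: "Assessment on or after ICEs will be treated missing and imputed assuming MNAR delta adjustment imputation". Section 14.1.1.3 adds deltas of 3, 4 and 5, applied only to efgartigimod participants with an ICE. Other missing efgartigimod data, and all missing placebo data, are imputed under MAR. SAP 3.4 accordingly describes the supplementary method as ANCOVA after MNAR imputation.

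After the sample imputation code, Section 14.1.1.3 states the fallback in one sentence. Its condition is that the imputation cannot be carried out because of the low numbers anticipated, either at the first interim or at the later analysis. The sentence then ends: "subsequently at week 24, the ANCOVA analysis will be undertaken on observed data only". The ANCOVA code that follows is annotated "i.e using week 24 data only".

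The main analysis is separate. It is an MMRM on all scheduled visits, using scores after an ICE as observed (SAP Section 2, 3.4 and 14.1.1.1).

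**The concern.** The supplementary analysis exists to show whether the main result survives a less favourable assumption about people who stop IMP or take prohibited medication. The fallback removes that assumption and names no estimand in its place. A reader of the report could take an observed-data result as the composite result.

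Three features add to this:

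- The trigger has no objective criterion, so whether imputation was possible would be decided with the data in hand.
- The fallback uses one visit, so it discards the partial histories that the MMRM keeps. The check would then rest on less information than the analysis it is meant to check.
- The check is most likely to be abandoned when many week 24 values are missing, which is when it is most wanted.

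**Working it through.** **1. Can the fallback estimate the composite estimand?** This is settled by setting the texts side by side. The answer depends on who has a week 24 score.

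| Participant | Planned composite analysis | Observed-only ANCOVA |
|---|---|---|
| No ICE, week 24 score present | Used | Used |
| No ICE, week 24 score missing | Imputed under MAR | Dropped |
| ICE, no week 24 score | Imputed | Dropped |
| ICE, week 24 score present, Section 2 rule kept | Set to missing, then imputed | Dropped |
| ICE, week 24 score present, Section 2 rule not kept | Set to missing, then imputed | Used as observed (treatment policy) |

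The last two rows are the two readings that the SAP leaves open. The first gives a complete-case analysis. The second gives the main estimand's strategy with a weaker method. Neither imputes a post-ICE outcome, so neither targets the composite estimand.

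**2. The SAP is not consistent on who is imputed.**

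- Section 2 sets every assessment on or after an ICE to missing.
- The ICE table in 14.1.1.3 imputes discontinuers who left the study. On that text, those who stayed keep their scores.
- The note beside the sample code limits the MNAR step to efgartigimod participants whose ICE is something other than stopping treatment. On that text, discontinuers receive no delta.

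Even on the ICE-table reading, leavers are imputed under the plan and dropped under the fallback.

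**3. Size of the omitted adjustment.** Inputs: delta 3 to 5 (SAP 14.1.1.3). The proportion *p* of the efgartigimod arm receiving the delta is not given, and the planning dropout rate is blacked out, so 10% to 30% is an assumption. Because the delta enters one arm only, it shifts the treatment difference by *p* × delta.

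| Assumed *p* | Delta 3 | Delta 4 | Delta 5 |
|---|---|---|---|
| 10% | 0.3 | 0.4 | 0.5 |
| 20% | 0.6 | 0.8 | 1.0 |
| 30% | 0.9 | 1.2 | 1.5 |

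This is the adjustment left out, not the whole bias. The rest depends on how the dropped participants would have scored.

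**4. Scale.** The plan's own half-width is blacked out, so it cannot be reproduced. Protocol 9.5 gives an SD of 15 and a correlation of at least 0.8; 42 participants at 2:1 is 28 and 14.

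- SD of change = 15 × √(2 × (1 − 0.8)) = 9.49
- Half-width = 1.96 × 9.49 × √(1/28 + 1/14) = 6.09 points
- Omitted adjustment as a share: 0.3/6.09 = 5% to 1.5/6.09 = 25%

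**5. Is infeasibility likely at week 24?** The sample code imputes placebo from placebo alone on the full visit history. For MaPS, "The visits included in the model will be weeks 2, 4, 8, 12, 18 and 24". The week 24 regression therefore has an intercept, baseline and five earlier changes: 7 coefficients. If 2 of 14 placebo values are missing (assumption), 12 − 7 = 5 residual degrees of freedom remain. For COMPASS 31, with three earlier visits, it is 12 − 5 = 7. Both can be fitted, though imprecisely.

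A pooled model with intercept, arm, baseline and last observed change has 4 coefficients. With about 8 of 42 week 24 values missing (20%, assumption), it keeps 42 − 8 − 4 = 30.

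**The case against.** The strongest reply is that the stakes are small. Only a supplementary analysis is touched, the trial tests no formal hypothesis, and inference rests on the precision of the MMRM estimate. The SAP also calls its code a sample that may be altered. All of that stands, and it limits the weight of the point.

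Some stronger inferences are tempting, but the documents do not support them:

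- **That the SAP expects imputation to fail.** What it expects is small samples; infeasibility is only a condition. The counts above show a fragile placebo model at week 24, not an impossible one. Failure is more plausible at the week 12 interim, where SAP 14.1.1 says the week 24 ANCOVA will hold only a subset of participants.
- **That the fallback removes exactly the people the estimand concerns.** The estimand covers the whole FAS. Protocol 7.1.1 encourages discontinuers to stay. Both questionnaires are also collected at the discontinuation visits, and the week 24 windows open at day 128 (COMPASS 31) and day 149 (MaPS). Some ICE participants can therefore have a week 24 score.
- **That the result would certainly be reported under the composite estimand's name.** The SAP specifies no label. The gap is that it does not require a different one.

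It is also fair to say that the choice of reduced model is a matter of judgement. None of this makes the observed-only ANCOVA an estimator of the composite estimand.

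**Conclusion.** The concern holds in a limited form. The fallback cannot deliver an estimand under which post-ICE outcomes are "imputed as gaining no further benefit over and above that of the control arm", whichever way observed post-ICE scores are treated, and the condition that triggers it is undefined. That conclusion follows from the text and needs no assumption about rates.

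Its numerical size does need one. The 0.3 to 1.5 points hold only for assumed efgartigimod ICE rates of 10% to 30%, and only if every such participant would have received the delta. Under the note beside the sample code, fewer would. The shift is modest beside the roughly 6-point half-width for COMPASS 31. The main MMRM result does not change. This is a cheap improvement, not a threat to the trial's principal conclusion.

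**What to change.** Amend SAP 14.1.1.3 before unblinding:

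1. **State the trigger.** Give an objective infeasibility rule, applied mechanically to each outcome and each analysis. Examples are that PROC MI fails to run, or that fewer than a stated minimum of observed week 24 values are available in an arm.
2. **Make a reduced imputation model the first fallback.** Pool both arms and use arm, baseline and last observed change, defining which visit supplies that change for participants who have a week 24 score. Keep the same ICE handling, deltas and Rubin combination.
3. **If that also fails, report the composite estimand as not estimable.**
4. **Label any observed-only ANCOVA as a separate analysis with a different estimand**, and state whether observed post-ICE scores are included.
5. **Reconcile Section 2, the ICE table and the note beside the sample code** on which ICE participants are set to missing and which receive the delta.

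The cost is SAP wording and a few lines of code. The downside is a simpler imputation model that uses less of the visit history.
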